- 2. Patients who have existing diseases that could cause breathlessness but have residual or increasing breathlessness that could be caused by other not yet detected diseases. Or HCP has doubts or requires additional tests to confirm diagnosis or to suspect new, parallel, diagnoses. For example, breathlessness in patients assessed:
 - a. within the framework of Cardiovascular Risk Management
 - b. for COPD monitoring

Patients with acute worsening of previous diagnosed chronic disease where there is no suspicion of comorbidities (for example when a patient with clear COPD diagnosis has an exacerbation where typically the HCP will not perform additional tests) will be excluded from the study.

Intervention: All general practices will start with a control period, during which healthcare professionals will obtain consent from eligible participants to collect data and perform consultations as usual. At a certain timepoint, defined by randomisation, they will be assigned to use BiaB. From this moment on, visiting patients that meet inclusion criteria will be asked to partake in the study. After consent, healthcare professionals will use BiaB during patient

consultations/diagnostic workup. The BiaB-box contains questionnaires (YEARS, PHQ-4), point of care tests (NT-proBNP, D-dimer, pulse oximeter), an oscillometer and an ECG device. The BiaB-App will guide the healthcare professional (clinician, nurse, practice assistant) through the steps of diagnostic procedures within the BiaB-box. The BiaB-algorithm, developed by the GPRI team in collaboration with the international scientific advisory board, uses input from these tests to support the healthcare professional with interpretation of test results and generates the BiaB-report.

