4.3 Sample size determination

The sample size was determined to reliably demonstrate that there is a difference in the number of days between presentation with breathlessness in the clinic and diagnosis of a disease or disorder causing this breathlessness between usual care and the BiaB intervention.

For stepped-wedge clustered designs, the sample size is a combination of the number of clusters, the number of sequences, the number of time periods and the number of individuals per cluster period.⁷ Research shows that the best method of estimating the required sample size for a

stepped-wedge design is to simulate the power based on the method of analysis proposed including time in the chosen model.^{8,9} Therefore, for this study a sensitivity analysis has been performed using a desired power of 80% for the test of the intervention, with a type I (two-tailed) error rate of 0.05. The analysis was performed using the US National Institute for Health Stepped-wedge Group-Randomized Trials (SWGRT) Calculator software.¹⁰

The following assumptions were considered:

- The expected cluster autocorrelation (between two consecutive periods at the cluster level) was estimated 0.8, as healthcare professionals (HCPs) will use standard protocols or guidelines which are not expected to change between consecutive (6 week) periods within the study period.
- The intra class correlation was set to 0.03 based on previous data.¹¹
- The expected individual autocorrelation (between two consecutive periods at the level of the patient) was estimated 0.8, as HCPs will use standard protocols or guidelines which are not expected to change between consecutive (6 week) periods within the study period.
- The decay-structure for over-time correlations is Block-exchangeable.
- The churn rate was set to 0.0, as the study consists of one visit for data collection and data essential for the primary objective can be retrieved from HCPs.
- The number of patients per sequence (3 practices) is 60.
- Variation in cluster size is not taken into account as 60 patients will be included per cluster for analyses.
- The expected distribution of the primary outcome, dichotomous was set to 0.3.
- There are 6 time periods (including usual care and BiaB intervention period).

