- The hypothesized intervention effect as a difference of time to diagnosis from presentation with breathlessness between usual care and BiaB intervention is 0.2 (20% reduction of time to diagnosis (in days) based on data from the BiaB pilot study, assumed differences between countries the assumption that the average time to diagnosis in usual care will be 70 days and the assumption that a reduction of 14 days is assumed clinically relevant). The 70 day period is chosen after discussions with the scientific advisory board,

including general practitioners, pulmonologists and cardiologist from the Netherlands, Spain and the United Kingdom, because after an extensive literature search, no timed pathway could be found. This 70 days is based on knowledge of access times to several diagnostic tests and clinical experience.

Calculations showed that with 60 patients per cluster (20 patients per site, 5 sequences, 3 countries) and 3 sites per sequence per country we have sufficient power to detect an absolute difference in effect of 0.055 and a standardized detectable difference of 0.114 (i.e. 5.5-11.4%, respectively).

When assuming the outcome as a continuous effect of 0.2 with a variance of 0.1, we would have sufficient power to detect an absolute difference in effect of 0.0362 and a standardized detectable difference of 0.1144 (i.e 3.6 and 11.4%).

In terms of feasibility, Okkes et al. show an average of 2 to 3 patients present with breathlessness per primary care facility in the Netherlands monthly,¹² and other research shows the prevalence of breathlessness is even higher in Spain.¹³ This means the determined study period is sufficient to find 20 patients to participate per site during the study.

5. BiaB procedures

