6.1.1 Primary study endpoint

The primary endpoint is days between presentation with or consultation for breathlessness and a diagnosis causing the breathlessness (usual care group versus BiaB intervention group).

Required variables:

- Date of presentation with breathlessness,
- Date of first consultation for breathlessness,
- Date of diagnosis, and
- Type of diagnosis.

Strategy: Data will be retrieved during patient consultation (presentation and consultation for breathlessness) and periodically (up to 12 months, to account for referral waiting times) from healthcare professional (HCP) reporting (date and type of diagnosis). The exact date of presentation with breathlessness, consultation and diagnosis will be recorded. If exact date of presentation is unknown, it will be set to [01/MM/YYYY], where MM is the month where symptoms started. If duration of presentation is >1 month and start date is unknown, it will be set to either [01/01/YYYY] or [01/07/YYYY] (whichever is most accurate). Date of diagnosis is defined as date of recorded diagnosis related to breathlessness by any HCP (either reported by

HCP or noted in referral documentation) or start of treatment related to breathlessness. If multiple diagnoses are recorded, all will be collected, and the first diagnosis is used to determine time to diagnosis. Patients with missing data will be censored. In countries where a preliminary diagnosis is entered int the medical records to make prescription of medication possible before diagnostic tests are performed, the date of diagnosis will be validated by the HCP to ensure final clinical diagnosis date.

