8.1.2 General considerations

To demonstrate whether BiaB use shortens time to diagnosis as compared to usual care, the time from presentation with breathlessness to diagnosis for breathlessness will be compared between the usual care group and the BiaB intervention group.

Time between presentation and diagnosis will be summarised as number of days (median with interquartile range) for patients in the usual care group and BiaB intervention group.

Additionally, analyses will be performed stratified per country and will be presented for the different study populations. The stepped-wedge study design, including potential clustering effects, will be considered in the analysis.

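### The primary endpoint has no single start date, and its fallback replaces presentation with symptom onset or with 1 January/1 July, an error that can exceed the 14-day target

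*Protocol*

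**What the plan says.** Protocol section 6.1.1 defines the endpoint thus: "The primary endpoint is days between presentation with or consultation for breathlessness and a diagnosis causing the breathlessness". It then lists the date of presentation and the date of first consultation as separate variables, without saying which one starts the clock. Section 8.1.2 uses presentation alone: "the time from presentation with breathlessness to diagnosis for breathlessness will be compared". Sections 1 and 4.3 place that presentation at the healthcare professional or in the clinic.

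Section 6.1.1 intends exact dates to be recorded and adds two fallbacks:

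- Month rule: "If exact date of presentation is unknown, it will be set to [01/MM/YYYY], where MM is the month where symptoms started".
- Half-year rule, for a duration above one month with an unknown start: "it will be set to either [01/01/YYYY] or [01/07/YYYY] (whichever is most accurate").

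Section 5 places the BiaB tests after a consultation for breathlessness. Section 4.1 admits patients with residual or increasing breathlessness on top of known disease. On enrolment after the switch, the Summary says: "From this moment on, visiting patients that meet inclusion criteria will be asked to partake in the study". The planning effect in section 4.3 is that "a reduction of 14 days is assumed clinically relevant", on the assumption that "the average time to diagnosis in usual care will be 70 days".

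**The concern.** Presentation to a professional, the enrolling consultation and symptom onset are three different events. In a patient with long-standing breathlessness they can lie months apart. The endpoint definition allows the first two, and the month rule brings in the third. Two sites following the text faithfully could record different primary outcomes for the same patient.

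Time before the consultation at which BiaB could be used cannot respond to BiaB. Including it adds spread and shrinks the effect as a proportion of the interval. If its length, or the share of imputed dates, differs between the usual-care and BiaB phases, it also biases the comparison. One route is a patient who first presents under usual care, remains undiagnosed and is enrolled after the practice switches. That patient's usual-care waiting time is then counted in the BiaB group.

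This is not detail left to the SAP: the protocol itself fixes the rules, and they conflict.

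**Working it through.** **Inputs.** From section 4.3: effect 0.2 × 70 = 14 days; two-sided 5% level and 80% power; variance 0.1 in the continuous version; ICC 0.03; cluster autocorrelation 0.8; 6 periods. From section 3: 5 sequences, 45 sites, 20 patients per site. Assumptions of this check: true dates are uniform over the year, and 1.0 on the protocol's scale means 70 days, so SD = √0.1 × 70 = 22.1 days.

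**The plan's own figure.** A generalised least squares variance for 15 clusters, with the same 60 patients measured in all 6 periods, individual autocorrelation 0.8 and 8 degrees of freedom, gives a standardised detectable difference of 0.1144. Then 0.1144 × √0.1 = 0.0362, as stated. In days this is 0.1144 × 22.1 = 2.5. The calculation has no term for error in the start date. It also treats each patient as measured in every period, whereas section 3 describes one visit. That is a separate matter, but it is why power below uses one measurement per patient.

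**Month rule.** Error = day of month − 1. Over 365 dates: mean 14.7 days, SD 8.8, maximum 30, never late. This is the error in dating onset; any gap from onset to presentation comes on top.

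**January/July rule, nearest anchor.** The error is roughly uniform over 182.5 days:

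- SD = 182.5/√12 = 52.7 days.
- Mean absolute error = 182.5/4 = 45.6 days; 45.6/14 = 3.3.
- Maximum by enumeration 92 days; 92/14 = 6.6.
- 84% of dates are off by more than 14 days.
- If only the two anchors of the same calendar year are allowed, mean absolute error is 68.6 days and the maximum 183.

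**One patient, three outcomes.** Suppose onset is 5 May with the exact date unknown, and consultation and diagnosis are both on 10 June. From true onset the interval is 36 days. The month rule gives 1 May, so 40 days. Duration exceeds one month, so the half-year rule can also be read to apply. Its nearer anchor, 1 July (57 days away against 124), gives −21 days; 1 January gives 160 days.

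**Power for 14 days, one measurement per patient.** For 45 sites, 20 patients each over 6 periods, the standardised SE is 0.0977. With a share f imputed by the January/July rule, SD = √(SD₀² + f × 52.7²) and z = 14/(0.0977 × SD). Power is given with the normal critical value 1.96 and with t on 43 degrees of freedom (45 − 2; critical value 2.017).

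| SD₀ (days) | f | SD | z | Power, normal | Power, t |
|---|---|---|---|---|---|
| 22.1 | 0 | 22.1 | 6.47 | >99% | >99% |
| 22.1 | 0.25 | 34.4 | 4.16 | 99% | 98% |
| 22.1 | 0.50 | 43.3 | 3.31 | 91% | 90% |
| 22.1 | 1 | 57.2 | 2.51 | 71% | 69% |
| 50 (assumed) | 0 | 50.0 | 2.87 | 82% | 80% |
| 50 | 0.25 | 56.5 | 2.54 | 72% | 70% |
| 50 | 0.50 | 62.4 | 2.30 | 63% | 61% |
| 50 | 1 | 72.6 | 1.97 | 51% | 48% |

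On the plan's own 0.1144 the detectable difference rises from 2.5 days to 3.9, 5.0 or 6.5 at f = 0.25, 0.5 or 1, still below 14.

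**Relative effect.** If the mean interval includes 30, 90 or 180 days before the consultation (assumed), a 14-day gain is 14/100 = 14%, 14/160 = 8.8% or 14/250 = 5.6%, not 20%. The difference in means stays 14 days.

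**The case against.** Exact dates are the default, and the January/July rule needs both a duration above one month and an unknown start. No share of affected patients is given, and complete imputation would contradict the stated intention. On the plan's own variance and detectable difference, the noise does not remove power for 14 days. The error is per patient while 14 days is a difference between means, so their ratio does not measure bias. The month rule's early shift largely cancels if it is used equally in both groups. All of this stands. It limits the size of the problem, but it does not settle which date starts the clock.

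A reader might infer three stronger points that the protocol does not support:

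- **Immortal-time bias.** Being undiagnosed at enrolment is a condition in both phases. It is delayed entry common to both groups, and no difference between them is shown.
- **Staff choosing dates in knowledge of the phase.** Section 6.1.1 does not say who applies the rule, and it asks for the more accurate anchor.
- **A known power loss.** The fall from about 80% rests on a 50-day SD that is not in the protocol.

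Section 5 collects symptom duration in the BiaB-app, while the usual-care schedule in Table 1 has no matching row. The share of unknown dates could therefore differ by phase. But section 6.1.1 plans to collect the dates at the consultation without distinguishing the phases, so this remains a possibility.

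It is also fair to say that the enrolling consultation is not the only defensible anchor. The recorded date of first consultation would also remove the ambiguity, but it would keep time that BiaB cannot affect.

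**Conclusion.** The point holds and should be settled before any data are analysed. Its weight rests on two features of the text: the primary endpoint has no single start date, and the fallback substitutes a different event or a coarse calendar date that can fall after the diagnosis. Neither depends on an assumed SD.

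The loss of precision is conditional on the unknown share imputed. It is slight if few dates are missing. If all were imputed by the January/July rule, power would be 69–71% at the protocol's variance or 48–51% at an SD of 50 days. These figures assume uniform true dates, nearest-anchor rounding and one measurement per patient; the 22-day SD also depends on reading 1.0 as 70 days. Bias between groups arises only if time before the consultation, or the use of imputation, differs between phases. The protocol allows for that but does not show it.

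**What to change.** - Define one time zero for both groups: the recorded date of the enrolling consultation for breathlessness at the study practice. State which visit counts when Visit 0 and Visit 1 fall on different days.
- Assign each patient to usual care or BiaB by the practice's phase on that date.
- Use neither the month rule nor the January/July rule for the primary endpoint.
- Keep symptom duration and date of first presentation as baseline descriptors or covariates.
- Report time from the recorded date of first consultation as a sensitivity analysis.
- Align sections 1, 4.3, 6.1.1 and 8.1.2 with this wording.

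The cost is protocol and SAP wording; no new data are needed. The price is a narrower estimand: delay before the enrolling consultation is reported separately, and the 70-day planning figure must be re-read as time from that consultation.

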6.1.2 Secondary study endpoints

6.1.2.1 First secondary endpoint

The first secondary endpoint is the number of new diagnoses of COPD and heart disease (CVD) in patients (usual care group versus BiaB intervention group).

Required variables:

- The number of newly diagnosed patients
- The number of new diagnoses
- The number of diagnoses per patient
- The number of patients presenting with breathlessness
- The type of diagnosis

Strategy: Data will be retrieved periodically (up to 12 months, to account for referral waiting times) from HCP reported outcomes (date and type of diagnosis). All types of diagnosis will be recorded. For determining the secondary endpoint, type of diagnosis will be categorized as either heart, respiratory, psychological, and other. In case no diagnosis is reported, this will be reported as late diagnosis. If multiple diagnoses are recorded, all will count towards the endpoint. In countries where a preliminary diagnosis is entered int the medical records to make prescription of medication possible before diagnostic tests are performed, the date of diagnosis will be validated by the HCP to ensure final clinical diagnosis date.

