Rationale: Breathlessness has a prevalence of ~10% and is a common reason for people to consult their general practitioner. As breathlessness is a symptom in various conditions it is difficult to determine its cause, which hampers optimal treatment. There is a lack of quick and easy tests that can be used in primary care to diagnose the cause of breathlessness. Therefore, we have developed "Breathlessness diagnostics in a Box (BiaB)", an easy and reliable tool intended to support healthcare professionals with fast execution of diagnostic procedures required to diagnose the cause(s) of breathlessness. In 2023 a pilot study was performed to design and test BiaB. In the current study, we aim to investigate whether implementation of BiaB in primary care will shorten the time for the diagnostic process for patients presenting with breathlessness.

Objectives:

Objectives	Endpoints				
Primary					
1. To demonstrate whether BiaB use	Days between presentation with or				
shortens time to diagnosis as compared to	consultation for breathlessness and a				
usual care without BiaB use.	diagnosis causing the breathlessness (usual				
	care group versus BiaB intervention group)				
Secondary					
2. To demonstrate whether BiaB use	Number of newly diagnosed patients with				
increases the number of new diagnoses of	COPD and heart disease (usual care group				
COPD and heart disease as compared to	versus BiaB intervention group)				
usual care without BiaB use.					
3. To demonstrate usability and efficiency	Frequency of use of:				
of BiaB.	• BiaB				
	 Lung function tests 				
	 ECG measurements 				
	Frequency of:				
	 Referral to specialist (and type) 				
	 Acute hospital admission 				
	 Emergency room visits 				

Clinical outcomes
Economic analysis
Qualitative evaluation of the implementation of BiaB

Study design: In this study the implementation of BiaB in primary care will be evaluated. A total of 45 practices (900 patients) will be included in the Netherlands, Spain, and Portugal, with the option to expand to other countries. A stepped-wedge study design will be used with a randomised timing of BiaB implementation in general practices. The design includes a control period of 6-30 weeks, a transition period of 4 weeks, and a BiaB period of 3-30 weeks. Each practice will actively participate in the study for 40 weeks.

Study population:

- 1. Patients with undiagnosed dyspnea (breathlessness)

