8.2.2 General considerations

All secondary analyses will be stratified per country and results will be presented for the different study populations. All results will be compared between the usual care group versus the BiaB intervention group. Data will be summarised as descriptive statistics (number of observations, mean, SD, median, interquartile range, minimum and maximum) where appropriate. The stepped-wedge study design, including potential clustering effects, will be considered in the analysis.

- To evaluate the number of newly diagnosed patients with COPD and/or heart disease
 (CVD) in patients with breathlessness, the following outcomes will be reported: frequency
 and cumulative incidence of new (working) diagnosis of COPD and/or heart disease.
- To demonstrate usability and efficiency of BiaB the following statistics will be reported:
 - Frequency of use of: BiaB, Lung function tests, ECG measurements,
 - The distribution of working diagnosis outcomes from the BiaB box,
 - Frequency of: Referral to specialist (and type), Acute hospital admission, Emergency room visits,
 - Clinical outcomes; BiaB report and advice, patient characteristics,
 And:
 - Economic analysis will be performed; reporting either cost-benefit or budget impact.

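### The coding rules for the first secondary endpoint do not match the endpoint: COPD is pooled with other lung disease, sections count different units, and 'late diagnosis' is undefined

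*Protocol*

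**What the plan says.** Section 6.1.2.1 opens: "The first secondary endpoint is the number of new diagnoses of COPD and heart disease (CVD) in patients". Its required variables include newly diagnosed patients, new diagnoses and diagnoses per patient. Its strategy paragraph then sets four rules:

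- On recording: "All types of diagnosis will be recorded".
- On grouping: "For determining the secondary endpoint, type of diagnosis will be categorized as either heart, respiratory, psychological, and other".
- On patients without a diagnosis: "In case no diagnosis is reported, this will be reported as late diagnosis".
- On patients with more than one: "If multiple diagnoses are recorded, all will count towards the endpoint".

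Elsewhere the unit varies. The objectives in the Summary and section 2, and the hypothesis in 8.2.1, speak of new diagnoses. The endpoint column of the Summary begins "Number of newly diagnosed patients with" and goes on to name COPD and heart disease. The analysis in 8.2.2 reads "To evaluate the number of newly diagnosed patients with COPD and/or heart disease" and reports a frequency and a cumulative incidence.

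**The concern.** These are coding rules that the protocol states, not details left open for the statistical analysis plan. Followed literally, they produce a count of heart and respiratory diagnoses, with several possible per patient. The hypothesis concerns COPD and heart disease, and the planned analysis summarises patients.

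Three things are at stake:

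- **Pooling.** Section 5.1.1 describes oscillometry as especially sensitive for obstructive disease, asthma included. If BiaB raises asthma diagnoses, the four-group coding cannot separate that from a rise in COPD.
- **Unit.** Outside the PE tests, a BiaB visit runs all the cardiac and lung tests together (section 5). If this uncovers more dual disease, counting diagnoses and counting patients can give different treatment effects.
- **Label.** Someone followed for 12 months without a diagnosis and someone who withdrew are different outcomes. Section 6.6 provides no follow-up after withdrawal, yet both would be reported under one name.

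Section 8 requires the formal analysis plan only before database lock, so these choices could be settled late. This is the only hypothesis in section 8 besides the primary one.

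**Working it through.** The protocol gives no sample-size or power figure for this endpoint (section 4.3 concerns the primary), so there is nothing to reproduce. The check is a comparison of texts, with a small illustration.

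**1. Categories against endpoint.** The endpoint needs two classes, COPD and heart disease. The rule supplies heart, respiratory, psychological and other. Heart maps across; COPD does not, and no rule leads from respiratory back to COPD. Section 6.1.3 lists COPD and asthma separately in both the differential diagnosis and the medical history, so the protocol makes the distinction elsewhere.

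**2. Unit.**

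| Place | Unit |
|---|---|
| Summary, objective | diagnoses |
| Summary, endpoint column | patients |
| Section 2 | diagnoses |
| 6.1.2.1, definition and counting rule | diagnoses |
| 8.2.1, hypothesis | diagnoses |
| 8.2.2, analysis | patients, with cumulative incidence |

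**3. Does the unit matter?** The inputs are the hospital dyspnea clinic figures quoted in section 1: heart failure alone 17%, pulmonary disease alone 35%, both 14%. Allowing at most one heart and one lung diagnosis per patient, per 100 patients:

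- Patients with at least one: 17 + 35 + 14 = 66.
- Diagnoses: 17 + 35 + 2 × 14 = 80.
- Ratio: 80 / 66 = 1.21.

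With 900 patients at 1:1, or 450 per condition, this is 0.66 × 450 = 297 patients against 0.80 × 450 = 360 diagnoses.

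**4. When does the unit change the comparison?** Let p be the proportion with at least one diagnosis and d the proportion with both. The patient ratio is p₁/p₀; the diagnosis ratio is (p₁ + d₁)/(p₀ + d₀). They agree when d/p is the same in both conditions, so a common 21% excess cancels from the ratio. They differ when the overlap share differs. As an assumption only, hold p at 66 per 100 in both conditions, keep d₀ = 14, and let d₁ range from 14 to twice that, 28. The patient ratio stays at 1.00. The diagnosis ratio runs from 80/80 = 1.00 to (66 + 28)/80 = 94/80 = 1.175.

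**5. Size of the pooled class.** On the same figures, respiratory disease would be present in 35 + 14 = 49 per 100, or about 220 of 450. The protocol gives no COPD share. For an assumed share of 25% to 75%, COPD would account for about 55 to 165 of them.

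**6. The label.** 'Late diagnosis' is not one of the four groups, is not defined, and carries no rule for the analysis. For the primary endpoint, section 6.1.1 censors patients with missing data instead.

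**The case against.** The strongest reply is that this is loose wording around a recoverable endpoint. Much of that stands, and it rules out several stronger readings that a reader might infer.

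- *The endpoint cannot be obtained.* Not supported. All diagnosis types are recorded, and 8.2.2 names COPD and heart disease, so COPD can be extracted. Doing so, however, means departing from the stated grouping rule.
- *Asthma will be credited as COPD.* No sentence equates respiratory with COPD. The text has a rule that fails to separate them, not one that substitutes one for the other.
- *Counting several diagnoses per patient is itself an error.* It agrees with the objectives, with 6.1.2.1's own definition and with the hypothesis. The fault is the conflict with the patient wording in the Summary's endpoint column and in 8.2.2. A cumulative incidence could be built from dated first diagnoses, but the counting rule does not say so.
- *The 'late diagnosis' label inflates the count.* It does not: such patients are in neither the COPD nor the heart disease class.
- *The endpoint is biased by 21%, or 57% of patients would be mislabelled.* Neither figure measures this endpoint. The overlap figures concern heart failure and all lung disease in a hospital clinic, are not restricted to new diagnoses, and the same counting rule applies to both conditions. The 57% in section 1 is from a UK database at two years. Finding more dual disease may also be a real effect of BiaB.

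Deferral to the analysis plan is a weaker reply. Section 8 is a summary, but the grouping and counting rules stand in the protocol, and a later plan would have to override one protocol section with another.

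**Conclusion.** The concern holds as a mismatch between the stated coding rules and the endpoint they are meant to determine. Three points need correction: the missing COPD class, the conflict between diagnoses and patients, and an undefined label that mixes absent with unknown outcomes. The first two change what is estimated if the text is followed literally; the third affects reporting and the handling of missing outcomes, not the COPD and heart disease count.

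No size can be given for this endpoint. The 80-against-66 illustration rests on background figures from another setting and a broader disease definition, and the COPD share and the overlap under BiaB are assumptions. Whether the two units would give different effects depends on whether BiaB changes the share of dual disease, which the protocol does not predict. The point should be corrected, but it does not threaten the design or the primary endpoint.

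**What to change.** 1. **Categories.** In 6.1.2.1, code COPD separately from other respiratory disease, and report COPD, heart disease and both.
2. **Unit.** Fix one unit across the Summary, section 2, 6.1.2.1, 8.2.1 and 8.2.2. One workable choice is patients with at least one new COPD or heart disease diagnosis, absent from the medical history in 6.1.3, within 12 months. This gives the first event that a cumulative incidence needs. Keep the total number of diagnoses as a supportive count.
3. **Label.** Replace 'late diagnosis' with 'no diagnosis by 12 months'. Keep patients who withdrew or were lost to follow-up apart, and censor them. Coding everyone without a reported diagnosis as a non-event would recreate the mixing.
4. **Related wording.** In the same edit, align 'and' with 'and/or', and the working diagnosis in 8.2.2 with the validated final diagnosis date in 6.1.2.1.

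The cost is protocol and analysis-plan wording. Diagnosis types and dates and the medical history are already collected, and no sample-size figure changes. The edit is best made before outcome data are seen.
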